
#### 19.2 Post registration discontinuations

Withdrawal information is collected on the Withdrawal and End of Treatment CRF.

Withdrawals from the study will be presented as line listings detailing:

- 1. Date of registration
- 2. Date of discontinuation of follow up
- 3. Number of days in the trial (Date of discontinuation of follow up date of registration (2-1))
- 4. Who made the decision to withdraw participant from trial:
  - a. Clinician
  - b. Participant
- 5. Reason and level for discontinuation:

#### Clinician:

- a. Death
- b. Participant transferred to a non-participating centre
- c. Serious Adverse Event (SAE)
- d. Other reason (specify free text to be categorised by CInv or delegated other)

  Participant level of withdrawal:
- a. Withdrawal of consent for ALL further follow-up
- b. Withdrawal of consent for OPTIONAL part/s of the study

#### Participant reason:

a. Free text reason to be categorised by Clnv or delegated other.

LIVERPOOL
CLINICAL
TRIALS CENTRE
LCTC

#### 20 Protocol Deviations

Protocol deviations that will be reported are defined and specified as minor or major within the monitoring plan [v1.0 16/05/2022] for the trial.

Patients to be excluded from analysis populations need to be defined in the template "LCTC\_ST003\_TEMP5: Protocol deviations and analysis set definitions for final statistical analysis report" and agreed and approved prior to analysis.

The number and percentage (denominator as number of patients registered) of patients with each separate protocol deviation will be presented in this analysis report along with the number and percentage (denominator as number of patients registered) of patients with:

- i. at least one major protocol deviation;
- ii. at least one minor protocol deviation;
- iii. at least one protocol deviation of any classification (minor or major).

These will also be summarised across site. No formal statistical testing will be undertaken.

#### 21 Unblinding

Not applicable since INCA is an open-label study.

#### 22 Analysis Datasets

#### 22.1 Efficacy Analyses

The primary and secondary outcome analyses will be conducted on all registered participants and for whom the outcome(s) of interest have been observed/measured. Patients who withdrew consent for trial continuation will contribute outcome data up until the point of withdrawal unless the patients' specifically request that the data are not to be used. No imputations will be made.

The membership of the analysis set for each outcome will be determined and documented and reasons for participant exclusion will be given prior to analysis. Reasons may include missing data, loss to follow up.

A per protocol analysis will not be performed, instead the occurrence of each protocol deviation will be monitored and sensitivity analysis performed as appropriate with patients experiencing deviations

of concern removed. The sensitivity analysis will apply to a secondary analysis of the primary outcome only.

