9 OUTCOMES

Primary Outcome

The proportion of patients with no serious or condition-specific AE's. Pre-determined potential condition-specific AE's include persistent pain at injection site (greater than 1 week) of at least moderate intensity (5 or greater on a 0-10 NRS scale) and increase in CRPS associated pain (>=2points NRS), ongoing for >1 month.

Secondary Outcome(s)

To identify any barriers to patient recruitment and retention:

- 1. Monthly registration rate.
- 2. The proportion of patients completing the study retention rate, and reasons for non-completion.

To obtain data that will enable a larger RCT to be designed in the future:

- 3. Change of pain intensity measured on a 0-10 point NRS from baseline (0 day) to 4 months/120 days after completion of Anakinra administration. Pain intensity at 120 days is defined for the purpose of this study a mean of the weekly scores and daily over the last month of drug administration. This is determined by calculating the results of the patient pain diaries.
- 4. CRPS severity score
- 5. Global Impression of change
- 6. Analgesic Medication use
- 7. EQ-5D 5L
- 8. Patient Health Questionnaire 9 (PHQ-9)
- 9. Brief Pain Inventory (BPI)
- 10. Hospital Anxiety and Depression Scale (HADS)
- 11. Skin sensitivity measured by mechanical quantitative sensory testing (QST)
- 12. Limb Volume (Figure of 8)
- 13. Work status

Table 3: Timepoints for objectives and outcome measurements

Objectives	Outcome Measures	Timepoint(s) of evaluation
To determine the safety/tolerability of Anakinra	Proportion of patients without SAEs	Baseline (0 day) -180 days
To identify barriers to recruitment and	Monthly registration rate	Baseline (0 day)
retention	Retention rate (proportion of patients completing study) and reasons for non-completion	Day 120/180
To obtain data that will enable a larger RCT to be designed in the future	Change of pain intensity measured on a 10-point NRS	Baseline (0 day) – day 120
	CRPS Severity Score	Baseline (0 day), 30, 60, 90, 120 days
	Global Impression of change (PGIC)	Day 120
	Change in Pain Interference measures: PHQ-9, BPI and HADS	Baseline (0 day), 30, 60, 90, 120 days
	EQ5D-5L	Baseline (0 day), 30, 60, 90, 120 and 180 days
	Skin sensitivity measured by Mechanical QST	Baseline (0 day) and day 120
	Limb volume (by figure of 8)	Screening visit, 60 day and 120 days
	Work status	Baseline (0 day) and day 120
	Analgesic Medication use	Baseline (0 day) and day 120

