10.9 Intervention Discontinuation and Participant Discontinuation/Withdrawal

In consenting to the trial, participants agree to all trial activities including administration of trial intervention and treatment and follow-up assessments/visits and data collection. Every effort should be made to facilitate the completion of these for every recruited participant. If it is not possible to complete these activities (or it is deemed inappropriate) the reasons why should be documented. The following sub-sections describe the different levels of discontinuation/withdrawal.

Premature Discontinuation of Trial Intervention

Participants may discontinue treatment for reasons including, but not limited to:

- Patient-led i.e. request by the patient / legal representative / consultee
- Unacceptable toxicity (see Section 13 for AE reporting)
- Intercurrent illness preventing further treatment.
- CRPS symptom progression which requires discontinuation of therapy or results in inability to continue to comply with study procedures
- Pregnancy
- Death
- Clinician-led:
 - Any change in the participant's condition that justifies the discontinuation of treatment in the clinician's opinion.
 - Reasons of non-adherence or non-compliance with treatment or other trial procedures
 - Participant meets an exclusion criterion (either newly developed or not previously recognised)
 - Participant unable to receive Anakinra for >=7 days consecutively

Discontinuation from Anakinra does not mean discontinuation of the study altogether, and the remaining study procedures, follow up assessment/visits and data collection should be completed as indicated in the protocol unless the patient requests to withdraw from further follow up visits. Data to be collected at the time of discontinuation will include the following:

- 1. Reason for discontinuation (if available)
- 2. Any AEs
- 3. Pain intensity score (NRS)

If a study participant is discontinued from the study early, an End of treatment CRF will be completed describing the reason for discontinuation. In situations where treatment is withdrawn due to an AE, participants will be followed up until resolution of that AE or determination that the participant's condition is stable. All AEs will be followed up until 180 day.

In case of a Participant Withdrawal the participant will be assessed for AEs, if any, and medication use.

Participant Withdrawal from Follow Up

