Participants are free to withdraw from follow up at any time without providing a reason, though a reason should be recorded if one is given. Those who wish to withdraw from further follow-up will have the data collected up to the point of that withdrawal included in the analyses. The participant will not contribute further data to the study unless this is required by law (e.g. safety events).

The LCTC should be notified of withdrawals from the study as soon as possible, a completed Withdrawal from Study CRF must be returned to the LCTC within 7 days.

In situations where study withdrawal is due to an AE, participants will be followed up until resolution of that AE or determination that the participant's condition is stable.

In case of premature discontinuation, the participant will be assessed for AEs, if any, and medication use.

Participant Transfer

If a patient moves from the area, every effort should be made for the patient to continue in the trial if they are happy to travel to site from their new location. If they are no longer able to continue with study visits (and therefore study treatment) every effort should be made by the site to follow up the patient as far as is possible. The trial provides financial support to participants of travel expenses of up to £20 per visit.

Loss to Follow-up

A participant will be considered lost to follow up if s/he fails to return for 2 scheduled visits and is not contactable by the site research team.

If a participant fails to attend/facilitate a required study visit the following actions must be taken:

- Site will attempt to contact the participant and reschedule the missed visit and advise the participant on the importance of maintaining the assigned visit schedule.
- Before a participant is deemed to be lost to follow up, site research staff will make every effort to regain contact with the participant (i.e. 3 telephone calls and, if necessary, a headed letter to last known address). These efforts should be recorded in the participants medical notes.
- If the participant continues to be unreachable they should be considered withdrawn from the study with a primary reason of lost to follow up and this should be recorded on the appropriate CRF.

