13.6 Time Period for Active Monitoring of Safety Events

IMPORTANT: Any safety events occurring after the end of the below-described "active monitoring" period which meet the definition of serious (see section 13.2) and are recorded for this study (see section 13.1) must continue to be reported by sites to the LCTC in accordance with the timeframes and procedures described in section 13.12. The same processes established for SAEs within the active monitoring period should be followed for these events.

Active monitoring of safety events experienced by trial patients will be carried out from the time of trial consent. Between the point of consent and baseline (Day 0) only safety events which are related to trial procedures will be monitored. Thereafter all safety events will be monitored, beginning with the baseline visit (0 Day), then every 30 days at clinic visits, and at all telephone calls between clinic visits until the 120 day visit (end of treatment). Further safety events will be monitored at the end of the study on day 180 which is 60 days after the last dose of Anakinra.

Pregnant women will be followed up until a completed outcome of pregnancy (see Section 13.8 for more information on reporting pregnancy).

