13.11 Reporting Safety Events to the LCTC

All safety events (whether or not assessed as serious / related / expected) should be recorded on an AE Form.

Safety events which are assessed as "serious" must **also** be recorded in more detail on SAE Forms; a single form is used for each individual event (i.e. a single diagnosis), though multiple symptoms can be recorded. Each SAE should have a corresponding record on the participant's AE form. Where additional information is received by site after initial submission to LCTC, this should be provided on a follow-up form within 5 days. SAE Forms collect data regarding the nature of event, date of onset, severity, corrective therapies given, outcome and causality; all serious events reported to LCTC will be reviewed by the CI or other Medical Reviewer, and assessed for causality and expectedness.

Follow-up After Adverse Events

All reportable AEs should be followed until satisfactory resolution or until the investigator responsible for the care of the participant deems the event to be chronic or the participant to be stable.

When reporting "serious" safety events the investigator responsible for the care of the participant should apply the following criteria to provide information relating to event outcomes:

- resolved
- resolved with sequelae (specifying with additional narrative)
- not resolved/ongoing
- ongoing at final follow-up
- fatal or unknown.

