#### 25.2.2.1 Derivation

This is defined as the proportion of patients with no serious or condition-specific AEs. Pre-determined potential condition-specific AEs are:

- Persistent pain at injection site (greater than 1 week) of at least moderate intensity (≥5 on a 0-10 NRS scale)
- Increase in CRPS associated pain (≥ 2points NRS), ongoing for >1 month.

Serious or condition-specific AEs are indicated on the following case report forms (CRFs) INCA Premature discontuation form, INCA Withdrawal form, Form 6: Follow up, Form 5: Telephone follow up and Form 7: Final telephone follow up. Further details of the events are collected on INCA Adverse Events form and INCA Serious safety event report form.

Patients will be classified as either having experienced at least one serious or condition-specific AE or experienced no serious or condition-specific AEs. The proportion of patients with no serious or condition-specific AEs will be defined as:

[total number of patients to have experienced no serious or condition-specific AEs]/[total number of registered patients].

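### The plan has no rule for a CRPS-pain rise that is still under one month old at the last contact, and both available readings treat it favourably in the primary safety proportion

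*SAP*

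**What the plan says.** **Event and window.** SAP 25.2.2.1 lists two condition-specific AEs. The one at issue is "Increase in CRPS associated pain (≥ 2points NRS), ongoing for >1 month". Protocol Table 3 (section 9) evaluates the safety objective over "Baseline (0 day) -180 days", although that row names only SAEs. Protocol 13.6 closes active monitoring at the same point: "Further safety events will be monitored at the end of the study on day 180 which is 60 days after the last dose of Anakinra".

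**Classification.** SAP 25.2.2.1 allows two classes, at least one serious or condition-specific AE or none, and divides by all registered patients. SAP 22.1 instead limits the primary analysis to registered participants whose outcome was observed, accepts missing data and loss to follow-up as reasons for exclusion, and imputes nothing.

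**How long an open AE is followed.**
- Protocol 10.9, on stopping treatment because of an AE: to resolution or a stable condition. The next sentence reads "All AEs will be followed up until 180 day".
- Protocol 10.9, on withdrawal from follow-up: "In situations where study withdrawal is due to an AE, participants will be followed up until resolution of that AE", or until the condition is stable.
- Protocol 13.11: "All reportable AEs should be followed until satisfactory resolution", or until the event is judged chronic or the participant stable. No calendar limit is given.
- SAP 22.1: "Patients who withdrew consent for trial continuation will contribute outcome data up until the point of withdrawal", with an exception only for patients who ask that their data not be used.
- SAP 11.3, repeating Protocol 10.9: no further data after withdrawal, except where the law requires it, with safety events as the example.

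**The concern.** An event defined by its duration needs a rule for cases where observation ends before the duration is reached. The plan has none for the CRPS-pain component. A participant who withdraws two weeks into a 2-point rise, or who reports at the day-180 call a rise that began on day 160, has a recorded worsening that does not yet meet the definition. With only two classes, that participant falls into the favourable one.

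The cases concerned matter for safety: people who leave soon after their pain worsens, and people who worsen in the second month off the drug. This is the primary outcome, and with 30 participants a few such cases would visibly shift the reported proportion.

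**Working it through.** **Inputs.** Last dose at day 120 and monitoring to day 180 (Protocol 13.6); visit window ±3 days (Protocol Table 4); duration more than 1 month, taken as 30 days with a range of 28–31; N = 30 (SAP 16).

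**1. The plan's own figure.** 120 + 60 = 180, so day 180 is reproduced.

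**2. Latest onset that can be confirmed if observation ends at day 180.** Latest onset = end of observation − required duration.
- 180 − 30 = 150.
- By month length: 180 − 31 = 149 to 180 − 28 = 152.
- With the visit window: 177 − 31 = 146 to 183 − 28 = 155.

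For someone last seen on day W, the same formula gives W − 30. A rise that began earlier than that has already met the definition and can be recorded on the withdrawal or premature discontinuation form that SAP 25.2.2.1 lists as a source.

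**3. Effect of the scoring rule.** Let e be participants with a confirmed event, and u participants with an unresolved rise and no other qualifying event.
- Scored as no event (SAP 25.2.2.1): (30 − e)/30
- Dropped (SAP 22.1): (30 − e − u)/(30 − u)
- Scored as events: (30 − e − u)/30

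The documents give no values for e or u. As an assumed illustration, take e = 3 and u = 2:

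| Rule | Proportion event-free | Exact 95% CI |
|---|---|---|
| No event | 27/30 = 90.0% | 73.5–97.9 |
| Dropped | 25/28 = 89.3% | 71.8–97.7 |
| Event | 25/30 = 83.3% | 65.3–94.4 |

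The gap between the first and third rules is u/30 whatever e is: 3.3, 6.7, 10.0 and 13.3 points for u = 1, 2, 3 and 4. Dropping gives almost the same figure as scoring no event.

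**4. Whether later data may settle the case.** Protocol 10.9 and 13.11 provide for collecting information beyond withdrawal or day 180. SAP 11.3 leaves room for safety events after withdrawal. SAP 22.1, which governs the primary analysis, stops outcome data at withdrawal and does not refer to SAP 11.3. One sentence of Protocol 10.9 stops at day 180. No section says that information collected later feeds the primary classification.

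**The case against.** The strongest reply is that the protocol already provides the missing observation. Someone who withdraws because of an AE is followed to resolution or stability, Protocol 13.11 follows every reportable AE without a calendar limit, and SAP 11.3 keeps safety events after withdrawal. Protocol 10.9 also says that stopping anakinra is not leaving the study. This largely stands, and it rules out one tempting inference: that rises starting late or leading to withdrawal cannot be observed for a month. Protocol 13.6 does not support that inference either, because its restriction to serious events concerns events that occur after monitoring ends, not those already open. What the reply leaves unanswered is whether the later information counts in the primary outcome.

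A reader might also infer that the conflicting follow-up end points create the day-150 limit. They do not. The limit follows from a one-month event in a window closing at day 180, and would remain if every section said day 180. The end points bear only on whether later data can settle the case.

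Two size claims should also be resisted. Thirty of 180 days is a sixth of follow-up, but reading that as a sixth of true events lost assumes uniform onset. Protocol 5.2.1 says most AEs are seen at 4 weeks, which points the other way. And the 50% completion threshold in Protocol 11 concerns treatment, not follow-up.

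The SAP 25.1.2.2 rule (pain at day X minus pain at day X − 30) might flag some late rises. It is written for the progression criterion, compares two dates without checking persistence, and is not carried into SAP 25.2.2.1.

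Finally, the study is descriptive, all AEs are tabulated whatever their duration (SAP 26), and a rise that is also serious counts at once. That limits the harm, but it does not correct the headline proportion.

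**Conclusion.** The point holds in a limited form. The plan does not say how to class a recorded rise of at least 2 points that has lasted less than one month at the last contact. SAP 25.2.2.1 read literally makes it event-free; SAP 22.1 may remove the participant. Relative to counting it as an event, both favour the drug, by up to 1/30 = 3.3 points per participant. If such a rise would in fact have settled within the month, the event-free class is correct, so 3.3 points is an upper limit and not an estimate of bias.

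The result assumes a 30-day month, all 30 participants registered, and no other qualifying event in the affected participant. The day-150 figure also assumes that observation for the primary outcome ends at day 180. The number affected cannot be derived from the documents. This is a cheap improvement to the primary safety outcome, not a defect that undermines the study.

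**What to change.** 1. **SAP 25.2.2.1.** Keep the protocol definition for the primary proportion. Add a class for *rise of at least 2 points, ongoing, duration not reached*, report its count, and show the proportion a second time with these participants counted as events. Recoding them in the main figure would change the protocol-defined outcome and is not proposed.
2. **SAP 22.1.** State, in line with SAP 11.3, that AE follow-up collected after withdrawal or after day 180 under Protocol 10.9 and 13.11 is used to settle whether a rise already open at that point lasted more than one month.
3. **Reconcile** the AE follow-up end points in Protocol 10.9, Protocol 13.11 and SAP 22.1, and the primary-outcome denominators in SAP 22.1 and 25.2.2.1.

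The cost is SAP wording, one extra class and one extra reported figure, plus whatever protocol clarification the reconciliation requires. No new visits are needed. It assumes that the AE form gives the onset and status of each rise. The small downside is that some short-lived rises will count as events in the second figure, which is the cautious direction for a safety outcome.

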14 STATISTICAL CONSIDERATIONS

14.1 Introduction

All baseline, primary and secondary outcome measures will be reported using appropriate summary statistical measures. There are no formal hypotheses evaluated in this study.

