14.2 Sample Size

A sample size of 30 has been estimated for this feasibility study. As this is a feasibility study, the sample size calculation can be difficult to determine.

Hertzog 2008 [38] recommends a sample size of between 20 and 40 patients for feasibility studies involving group comparisons. Hertzog suggests 30-40 patients per group will be required to yield confidence intervals whose lower limits can help define the range of plausible values for a subsequent power analysis.

Whitehead et al. 2016 [39] produced methods of calculating the optimal solution and approximate rules. For a main trial designed with 90% power and two-sided 5% significance, Whitehead et al. recommends a feasibility trial sample size per treatment arm of 75, 25, 15 and 10 for standardised effect sizes that are ≤0.1 (extra small), 0.2 (small), 0.5 (medium) and 0.8 (large) respectively.

The results of this feasibility study of 30 patients (single arm) will serve as data for sample size calculations for a further study. There are ethical and economic reasons for keeping this study population small, however the study results need to provide enough information to fulfil the specified primary and secondary endpoints.

With these reasons in mind and the recommendations of the two reference papers above, a sample size of 30 patients will be used for the INCA feasibility study.

The main outcome that will contribute to data for subsequent studies will be based on changes in pain intensity as measured by NRS (see Section 9). Feasibility data regarding the potential effects of Anakinra on pain intensity will be used to inform the sample size for the next stage of the study. The primary outcome of safety (throughout the study) and recruitment will be used to assess the rationale and feasibility of performing a larger RCT.

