14.4.1 Patient Groups for Analysis

Full Analysis Set

In order to follow the Intention To Treat (ITT) principle this will consist of all eligible and registered participants at baseline (0 day), excepting for: a) participants withdrawing consent between baseline (0 day) and starting therapy; b) participants withdrawn from the study after baseline (0 day) because of irregularities with the consent process; c) participants whose information determining ineligibility existed before registration but was not read until after registration.

Safety Set

All participants who received at least one dose of the trial treatment.

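### SAP 22.1 lets a withdrawn participant's collected data go unused on request, against protocol 10.9, SAP 11.3 and the all-registered denominator in SAP 25.2.2.1; if applied to a harmed participant, it raises the primary event-free proportion

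*SAP*

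**What the plan says.** Six places in the two documents bear on this.

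- **SAP 22.1 (Efficacy Analyses).** Despite its heading, it covers the primary outcome: "The primary and secondary outcome analyses will be conducted on all registered participants and for whom the outcome(s) of interest have been observed/measured". Participants who withdraw consent contribute data "up until the point of withdrawal unless the patients' specifically request that the data are not to be used". It adds: "No imputations will be made".
- **Protocol 10.9.** "Those who wish to withdraw from further follow-up will have the data collected up to the point of that withdrawal included in the analyses". No opt-out is stated. SAP 11.3 repeats the sentence.
- **Protocol 14.4.1 (Full Analysis Set).** All eligible registered participants, with three exclusions. The first reads "excepting for: a) participants withdrawing consent between baseline (0 day) and starting therapy"; the others are consent irregularities and ineligibility information that existed before registration but was read afterwards. A request that data not be used is not among them.
- **SAP 25.2.2.1.** The primary proportion is "total number of patients to have experienced no serious or condition-specific AEs]/[total number of registered patients".
- **SAP 22.2.** The safety set is everyone registered who took at least one dose, with no data-use exception.
- **SAP 26.** All reported adverse events and SAEs are tabulated, again with no exception.

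SAP section 5 says the planned analyses comply with protocol v6.0. The protocol's amendment log shows no later change to section 10.9 or 14.4.1.

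**The concern.** The primary outcome is a safety proportion, and the data at issue are already collected. A rule that removes observed data at the participant's request can act on the outcome itself, because someone who had a serious or condition-specific event is a plausible person to make that request. For such a participant the effect has only one possible direction: the event-free proportion stays the same or rises. The primary result could then also disagree with the section 26 tables, where the event would still appear.

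The texts leave the analyst to choose. One rule keeps the data, another drops them on request, and the primary formula divides by all registered patients. That choice should be settled before the data are analysed. The form for recording withdrawals does not help: SAP 19.2 gives two participant withdrawal levels, all further follow-up or optional parts, and neither records a refusal to let existing data be used.

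**Working it through.** **Inputs**

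- N = 30, single arm (protocol 14.2: "a sample size of 30 patients will be used for the INCA feasibility study"). This figure was chosen from published guidance on pilot studies. No alpha, power or precision target lies behind it (protocol 14.1: "There are no formal hypotheses evaluated in this study"), so there is no plan figure to reproduce.
- h = number of participants with a serious or condition-specific event. Not given in the documents; assumed 1, 3, 6 or 9.
- w = number of those h who ask that their data not be used. Not given; assumed 1, with 2 and 3 shown once.

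**Formulas**

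- A. Data kept (protocol 10.9, SAP 11.3): (30 − h)/30.
- B. Participant dropped from the set (SAP 22.1): (30 − h)/(30 − w).
- C. Participant kept in the all-registered denominator with the event record unused, and so counted as event-free: (30 − h + w)/30.

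If the all-registered denominator applies and the participant is not counted as event-free, the result equals A. The numerator counts people without an event, so a harmed participant is never in it, and B changes only the denominator.

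**Results with w = 1**

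| Harmed (h) | A: kept | B: dropped | B − A (points) | C: counted event-free |
|---|---|---|---|---|
| 1 | 29/30 = 96.7% | 29/29 = 100.0% | 3.3 | 30/30 = 100.0% |
| 3 | 27/30 = 90.0% | 27/29 = 93.1% | 3.1 | 28/30 = 93.3% |
| 6 | 24/30 = 80.0% | 24/29 = 82.8% | 2.8 | 25/30 = 83.3% |
| 9 | 21/30 = 70.0% | 21/29 = 72.4% | 2.4 | 22/30 = 73.3% |

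With h = 3 and more than one request, B gives 27/28 = 96.4% for w = 2 and 27/27 = 100% for w = 3, against 90.0% with data kept.

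**Precision, for scale.** Exact (Clopper-Pearson) 95% intervals are 73.5 to 97.9% for 27/30 and 77.2 to 99.2% for 27/29.

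**A requester without an event.** With h = 3 and one of the 27 event-free participants asking for non-use, dropping that person gives 26/29 = 89.7%. Keeping them in the denominator but not counting them as event-free gives 26/30 = 86.7%. So the clause does not raise the proportion for every requester. It does so when a harmed participant is dropped or is counted as event-free.

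**The case against.** The strongest reply is that SAP 25.2.2.1 is the text specific to this outcome and divides by all registered patients. Read literally, the illustration stays at 27/30 = 90.0% and 27/29 never arises. This stands in part. The loss from the denominator requires 22.1 to prevail, and the SAP does not say that it does. Equally, it does not say that 25.2.2.1 prevails, while 22.1 expressly claims the primary outcome. Even the literal denominator leaves open how an unused record is classified, and 28/30 is one possible answer.

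Second, protocol 10.9 and SAP 11.3 may be read as a default that does not address an express request. That makes the conflict a gap rather than two opposite rules, but the gap still has to be closed, and the protocol's list of exclusions leaves such requests out.

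Third, removal would not be silent. SAP 22.1 requires set membership and reasons to be documented before analysis, SAP 20 requires exclusions to be agreed and approved, and the SAP 19 flow diagram shows registered participants excluded from the primary analysis, with reasons. This stands, and it limits the harm. It makes the exclusion visible without reversing its effect on the reported proportion.

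Fourth, the shift is small beside the interval, the study tests no hypothesis, and the interim safety summaries in SAP 25.1.2.2 use the number registered. This also stands: no decision rule is shown to change.

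A reader might infer that a harmed participant leaves both numerator and denominator, or that the event disappears from all safety reporting. The documents support neither. The numerator holds only event-free participants, and SAP 22.2 and 26 have no opt-out. The statement in protocol 10.9 and SAP 11.3 about safety events required by law concerns further data after withdrawal, so it does not settle how data already collected are used.

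**Conclusion.** The inconsistency is real and reaches the primary outcome. SAP 22.1 contains a data-use opt-out that is absent from protocol 10.9, SAP 11.3 and the protocol's full analysis set, and it does not fit the denominator in SAP 25.2.2.1. Applied to a harmed participant, it can never lower the reported event-free proportion. It raises it if the person is dropped or counted as event-free, by 2.4 to 3.3 points per dropped participant at N = 30 with 1 to 9 harmed and one request.

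Those counts are assumptions, as is any tendency of harmed participants to make such requests; the documents do not say how often requests occur. It would go too far to conclude that the primary result will be biased, since that depends on a request being made and on which section is followed. The point is worth settling because the outcome is safety and the correction is small. It does not threaten the study's design.

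**What to change.** Align SAP 22.1 with protocol 10.9, SAP 11.3 and SAP 25.2.2.1 by deleting the opt-out clause. At the least, state that it does not apply to the primary safety outcome, whose denominator stays all registered patients with events observed before withdrawal counted.

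The consent pages were not available for this review, so the sponsor should first check what participants were told about use of their data. If the consent terms require an opt-out:

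- amend protocol 10.9 and SAP 11.3 to match;
- record and report the number of such requests, which needs a category in SAP 19.2;
- show the primary proportion over all registered patients, with those participants not counted as event-free.

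The first route costs one clause in the SAP. The second needs a protocol amendment, a SAP revision and one added withdrawal category. Neither needs new patients or visits.
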